9.7.2. Analysis of primary endpoints

The analyses of primary endpoints will be based on the SAS, and following will be presented:

Number and percentage of patients experiencing at least one AE/SAE with explicit attribution to nirmatrelvir/ritonavir will be summarized.

Summary of AEs/SAEs by SOC and PT in accordance with the Medical Dictionary for Regulatory Activities (MedDRA) will be provided; and AEs/SAEs will also be summarized by PT in descending order.

Number and percentage of patients with nirmatrelvir/ritonavir dose change (discontinuation/dose reduction) due to AEs with explicit attribution to nirmatrelvir/ritonavir will be summarized.

Number and percentage of patients experiencing safety related scenarios involving drug exposure (described in section 9.3 and 11) will be summarized in descending order.

9.7.3. Analysis of secondary endpoints

9.7.3.1. Analysis of treatment pattern endpoints

The analyses of treatment pattern endpoints will be based on FAS, and the following will be presented:

Number and percentage of patients receiving nirmatrelvir/ritonavir treatment only, and receiving nirmatrelvir/ritonavir plus concomitant COVID-19 related treatments, regardless of other concomitant medication, will be summarized.

The treatment duration (days) of nirmatrelvir/ritonavir will be summarized using n, mean, median, minimum, maximum, SD, and the 25th and 75th percentiles. This duration will also be categorized and be summarized using number and percentage for each duration category.

Number and percentage of patients receiving concomitant COVID-19 related treatments (described in section 9.3.5) will be summarized by therapeutic use (including antiviral therapy, immunotherapy, and other).

The treatment duration (days) of concomitant COVID-19 related treatments will be summarized using n, mean, median, minimum, maximum, SD, and the 25th and 75th percentiles by therapeutic use (including antiviral therapy, immunotherapy, and other), and also by subcategories of therapeutic use as listed in Section 9.3.5.

Number and percentage of patients receiving concomitant medications other than COVID-19 related treatments will be summarized by drug class.

9.7.3.2. Analysis of effectiveness endpoints

The analyses of effectiveness endpoints will be based on EAS1 and EAS, and the following will be presented:

Proportion of patients with COVID-19 disease severity (described in section 9.3.2) progressed or death from any cause and corresponding 95% CI will be summarized.

Time to alleviation of all targeted COVID-19 signs and symptoms (described in section 9.3.7) will be summarized by K-M plots with the median time and corresponding 95% CI.

Number and percentage of patients with two consecutive negative SARS-CoV-2 test results / CT \geq 35 (specimens collected in two different calendar days) and corresponding 95% CI will be summarized for the patients with at least two SARS-CoV-2 tests after treatment initiation.

Time to the first negative SARS-CoV-2 test result / CT \geq 35 from two consecutive negative SARS-CoV-2 test results / CT \geq 35 (specimens collected in two different calendar days) among patients with at least two SARS-CoV-2 tests (described in section 9.3.8) will be summarized and plotted in a K-M curve with the median time and corresponding 95% CI.

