 - Prior COVID-19 related treatments and other prior medications

Data sources

Individual-level data will be retrospectively abstracted from the HIS and LIS to the electronic Case Report Form (eCRF). Source documents may include but are not limited to electronic/paper medical records, prescription files, and laboratory testing results. No personal identifiable information will be abstracted. Only de-identified data will be used in analysis.

Study size

There is no formal hypothesis testing for this study. This study is planned to include approximately 1000 individuals who initiated nirmatrelvir/ritonavir between 11 February 2022 and 31 August 2022.

The primary objective of the study is to describe real-world safety of nirmatrelvir/ritonavir, and one of the primary safety endpoints is the proportion of patients experiencing AEs with explicit attribution to nirmatrelvir/ritonavir. With a sample size of 1000 individuals, there will be a probability of >99.9% to observe an AE related to nirmatrelvir/ritonavir with a low incidence rate of 1% in at least one patient, and a probability of 95.0% to observe an AE related to nirmatrelvir/ritonavir with an even lower incidence rate of 0.3% in at least one patient.

For effectiveness consideration, assuming 20% of patients will have two consecutive negative SARS-CoV-2 test results from two consecutive respiratory specimens collected in two different calendar days, and accounting for non-evaluable data loss, samples of 800 and 500 evaluable individuals will provide a 95% CI with a half width of 2.77% and 3.50%, respectively.

Data analysis

This study is descriptive in nature and no formal hypothesis testing will be conducted. Individual level data from all sites participating in the study will be pooled for analysis. One interim analysis is planned to be conducted and the report is expected to be available in May 2023 to provide timely summary and analysis based on available data.

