9. RESEARCH METHODS

9.1. Study design

This is a multicenter, single-arm, retrospective observational study to describe the safety, treatment patterns and effectiveness of nirmatrelvir/ritonavir among patients with COVID-19 in China. Approximately 5 hospitals and 1000 patients are planned to be included in this study. Retrospective data abstraction will start after site ethics committee approval. Patients who initiated nirmatrelvir/ritonavir treatment between 11 February 2022 and 31 August 2022 will be included in this study. Continuous recruitment of patients in each site will be employed. For analyzing purpose, the index date for an individual patient is defined as the date of initiating nirmatrelvir/ritonavir treatment. The baseline period for an individual patient is defined as the period from the first day of hospitalization through the index date to capture the patient's baseline clinical characteristics, medical history, and comorbidity. The observation period for an individual patient is defined as the period from initiation of nirmatrelvir/ritonavir (i.e., index date) until discharge from hospital, death, or a maximum of 28 days after the last dose of nirmatrelvir/ritonavir, whichever comes first. The study data cut-off date will be 02 October 2022. Each patient will be included in the study only once. If the patient initiated nirmatrelvir/ritonavir treatment more than once between 11 February 2022 and 31 August 2022, only the first treatment course will be included for analysis. The study design schematic is presented in [Figure 1](#).

Figure 1. Study design schematic

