9.3. Variables

This study will retrospectively abstract individual-level data from the HIS and LIS, which include electronic/paper medical records, prescription files, and laboratory testing results. Data for baseline variables will be abstracted from the baseline period. Data for primary and secondary endpoint variables will be abstracted from the observation period.

Table 1. List of variables and operational definitions

Variable	Role	Data source(s)	Operational definition
Age	Demographics /subgroup identifier	HIS	Age on index date. Age = Year of index date - Birth year See section 9.3.1 Risk factors for more detail.
Sex	Demographics	HIS	As recorded in medical record (male or female).
BMI	Baseline clinical characteristics / subgroup identifier	HIS	As recorded in medical record for individual height and weight or BMI. BMI = weight (kg) / [height (m)] ² . According to the WHO standard, four categories of BMI (kg/m ²) are underweight (<18.5), normal weight (18.5 ≤ BMI < 25.0), pre-obesity (25.0 ≤ BMI < 30.0) and obesity (≥ 30.0). ²¹ According to China guideline, four categories of BMI (kg/m ²) are underweight (<18.5), normal weight (18.5 ≤ BMI < 24.0), pre-obesity (24.0 ≤ BMI < 28.0) and obesity (≥ 28.0). ²² The assessment on or closest to the index date will be used. Both BMI categorizations will be used for analysis. See section 9.3.1 Risk factors for more detail.

PFIZER CONFIDENTIAL

090177e19c018db1\Approved\Approved On: 07-Dec-2022 08:12 (GMT)

Table 1. List of variables and operational definitions

Variable	Role	Data source(s)	Operational definition
Smoking status	Baseline clinical characteristics / subgroup identifier	HIS	As recorded in medical record. See section 9.3.1 Risk factors for more detail.
COVID-19 severity at baseline	Baseline clinical characteristics / subgroup identifier	HIS	COVID-19 severity will be categorized into four levels. Apart from categories of severity level, severity scale used and the relevant parameters used for severity assessment will also be abstracted from medical records. See section 9.3.2 COVID-19 severity for categorization and parameters in detail. The assessment of severity level on or closest to the index date will be used.

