9.3.7. Time to alleviation of all targeted COVID-19 signs and symptoms

The targeted signs and symptoms of COVID-19 (described in section 9.3.3) will be used for the analysis of time to alleviation calculation. For a patient, the targeted signs and symptoms recorded in either baseline or observation period will be evaluated.

The First Alleviation Date for a targeted sign/symptom is the date when alleviation is firstly recorded in medical records during the observation period

Event Date = The last date of (The First Alleviation Dates for ALL targeted signs/symptoms to be evaluated)

The time to alleviation of all targeted COVID-19 signs and symptoms is defined as:

- For a patient with the Event Date, it will be calculated as (Event Date) – (Index Date) +1.
- For a patient without the Event Date, it will be calculated as (End of Observation Date) – (Index Date) +1 and be considered as a censoring time. ^{7 12}

9.3.8. Time to two consecutive negative SARS-CoV-2 test results / CT ≥ 35

For patients with at least two SARS-CoV-2 tests (specimens collected in two different calendar days) after treatment initiation during observation period, the first day of a negative SARS-CoV-2 test / CT ≥ 35 from two consecutive negative results is considered as an Event Date.

The time to event of two consecutive negative SARS-CoV-2 test results / CT ≥ 35 in this study is defined as:

- For a patient with the Event Date, it will be calculated using (Event Date) – (Index Date) +1.
- For a patient without the Event Date, it will be calculated as (End of Observation Date) – (Index date) + 1 and be considered as a censoring time.

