9.5. Study size

There is no formal hypothesis testing for this study. This study is planned to include approximately 1000 individuals who initiated nirmatrelvir/ritonavir between 11 February 2022 and 31 August 2022. The primary objective of the study is to describe real-world safety of nirmatrelvir/ritonavir, and one of the primary safety endpoint is the proportion of patients experiencing AEs with explicit attribution to nirmatrelvir/ritonavir.

With a sample size of 1000, there will be a probability of >99.9% to observe an AE related to nirmatrelvir/ritonavir with a low incidence rate of 1% in at least one patient, and a probability of 95.0% to observe an AE related to nirmatrelvir/ritonavir with an even lower incidence rate of 0.3%²⁹ in at least one patient.

Table 4. Probabilities to observe an AE of different incidence rates

	Incidence rates		
Sample Size	1%	0.5%	0.3%
1000	> 99.9%	99.3%	95.0%

Note: The sample size and power is calculated based on the exact probabilities of the Binomial distribution, the probability of observing at least one event in n observations = $1 - (1-p)^n$.

For the effectiveness endpoint of proportion of patients with two consecutive negative SARS-CoV-2 test results, assuming that 20%³⁰ of patients will have negative SARS-CoV-2 test results from two consecutive respiratory specimens collected in two different calendar days, and 80% and 50% patients will be evaluable with at least one of the effectiveness endpoints data collected and in addition having at least one risk factor, samples of 800 and 500 individuals will provide a 95% CI with a half width of 2.77% and 3.50%, respectively.

Table 5. Precision for evaluating effectiveness for different numbers of evaluable patients

Scenarios	Evaluable patients	Half width of CI *
Included patients who had mild or moderate COVID-19 illness and had at least one risk factor at baseline for progression to severe COVID-19	500	3.50%
Included patients who had at least one of the effectiveness variables collected.	800	2.77%

*Note: The half width confidence interval is calculated according to the formula $z * \sqrt{p * (1 - p) / n}$, where $z = 1.96$ for a confidence level (α) of 95%, p = proportion, n = #of evaluable patients.

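### The viral-clearance percentage has no common assessment day, and patients unresolved at discharge count as not cleared in it but are censored in the Kaplan-Meier analysis, so it depends on length of stay

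*Protocol*

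**What the plan says.** **Endpoint.** Protocol section 9.7.3.2 reports the "Number and percentage of patients with two consecutive negative SARS-CoV-2 test results" or CT ≥35, with a 95% CI. The denominator is restricted: the result "will be summarized for the patients with at least two SARS-CoV-2 tests after treatment initiation". Neither this section, nor the endpoint list in 9.1.2, nor the abstract gives a day for the assessment.

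**Follow-up.** Section 9.3 states: "Data for primary and secondary endpoint variables will be abstracted from the observation period". Section 9.1 runs that period from the index date "until discharge from hospital, death, or a maximum of 28 days after the last dose of nirmatrelvir/ritonavir, whichever comes first".

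**Time-to-event version.** Section 9.3.8 takes the same event in the same kind of population: "For patients with at least two SARS-CoV-2 tests (specimens collected in two different calendar days) after treatment initiation during observation period". The event date is the first of the two negatives. A patient without an event date is given the time to the end of observation, "and be considered as a censoring time". Section 9.7.3.2 presents this as a Kaplan-Meier curve with the median and its 95% CI.

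**Planning value.** The abstract plans precision by "assuming 20% of patients will have two consecutive negative SARS-CoV-2 test results from two consecutive respiratory specimens collected in two different calendar days", and section 9.5 repeats the 20%. No day is attached to it. Section 9.5 then states that "samples of 800 and 500 individuals will provide a 95% CI with a half width of 2.77% and 3.50%, respectively".

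**The concern.** A percentage of patients who reach an event needs a time horizon. Here the horizon is each patient's own observation period, which discharge can end at any point up to the cap. Take a patient with two positive swabs on days 2 and 3 who is discharged on day 4. In the percentage this patient is a non-event, exactly like a patient still positive after four weeks. In the Kaplan-Meier analysis the same patient is of unknown status after day 4.

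This is the only effectiveness endpoint for which section 9.5 plans precision, so the printed CI will suggest a sharply estimated quantity. Section 9.7.4 also plans effectiveness subgroups by baseline severity, vaccination, risk factors, and renal and hepatic impairment. Several of these could plausibly affect length of stay, so a difference in the percentage between subgroups could reflect observation time and not speed of clearance. The limitations in section 9.9 do not mention variable follow-up.

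**Working it through.** **1. The plan's own figures.** Inputs from section 9.5: p = 0.20, z = 1.96, n = 800 or 500, half width = z·√(p(1−p)/n).
- n = 800: 1.96·√(0.16/800) = 2.77%, as stated.
- n = 500: 1.96·√(0.16/500) = 3.506%, stated as 3.50%.

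The arithmetic reproduces apart from truncation. The problem is what the 20% refers to.

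**2. How the planned 20% moves with length of stay.** Assumptions, none of them in the protocol: constant clearance hazard, discharge unrelated to clearance, one common observation length L, and L₀ the length at which 20% have cleared. Then the percentage is 1 − 0.8^(L/L₀).

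| L/L₀ | Percentage | Shift from 20% |
|---|---|---|
| 0.5 | 10.6% | −9.4 points |
| 0.75 | 15.4% | −4.6 points |
| 1.25 | 24.3% | +4.3 points |
| 1.5 | 28.4% | +8.4 points |
| 2 | 36.0% | +16.0 points |

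Clearance speed is the same in every row. A 25% change in stay already exceeds both planned half widths.

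**3. Observed percentage against a fixed-day figure.** Simulation of 200,000 patients: daily tests from the index day, constant daily clearance probability with median 6 days, stay of at least 2 days (2 plus a Poisson number), discharge independent of clearance. The minimum stay gives every patient two tests on different days, so the denominator rule is met. The true proportion cleared by day 7 is 55.6% throughout.

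| Mean stay (days) | Observed percentage | K-M day 7, censored at end of observation (9.3.8) | K-M day 7, censored at last confirmable day |
|---|---|---|---|
| 5 | 35.8% | 44.2% | 55.5% |
| 7 | 48.5% | 50.9% | 55.7% |
| 10 | 62.9% | 54.5% | 55.6% |
| 14 | 75.9% | 55.5% | 55.6% |
| 21 | 88.9% | 55.6% | 55.6% |

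The observed percentage moves by 53 points (88.9 − 35.8) with no change in clearance. The third column shows a second problem. The event date is the first negative, but it needs a later confirming negative. A patient censored on the discharge day is therefore counted as at risk on a day when no event could be confirmed, which pulls the early estimate down when stays are short.

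**4. The opposite case: discharge waits for clearance.** Same simulation, with patients leaving on the confirming negative and a cap at day 33. The observed percentage is 97.6% for a median clearance of 6 days and 89.2% for 10 days. If 30% of patients have a separate administrative discharge date, it is 87.2% and 76.1%.

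**The case against.** The strongest reply has four parts.

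- *The two summaries do not contradict each other.* One is an observed proportion by end of observation, the other a time-to-event estimate, and reporting both is ordinary descriptive practice. The percentage does have a window, with a cap. This stands: what is missing is a common day, and a label saying what the figure means.
- *The Kaplan-Meier curve already answers the question, and choosing landmark days belongs to the SAP.* This stands in part. A value can be read off the curve, but the protocol itself fixes the endpoint, denominator, summary statistic and censoring rule, and the only time-to-event estimate it names with a CI is the median. The percentage would still be reported as a separate result.
- *The study is single-arm and descriptive, and clearance is a secondary endpoint.* This stands and limits the weight of the point to interpretability.
- *Kaplan-Meier is not automatically better.* This stands. If discharge depends on test results, censoring at discharge is informative. It is a reason to keep the observed percentage beside the fixed-day estimates.

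A reader might go further and infer that every patient who leaves early is counted as a failure. The protocol does not support that: patients with fewer than two post-initiation tests are in neither analysis. That exclusion is itself a dependence on testing and discharge practice, but it changes the numbers. Take lognormal clearance (median 9 days, log-SD 0.4) and an independent exponential stay with median 7, 14 or 21 days, capped at 33. Over all patients the percentage is 41%, 63% or 73%. Among those observed for at least 2 days it is 50%, 69% or 78%, and for at least 3 days 55%, 73% or 81%. The first set does not describe the protocol's denominator.

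A reader might also infer that the percentage must understate clearance. That rests on discharge being independent of clearance. The rationale (section 7) says test-positive patients are admitted for treatment or quarantine, which makes a link between negative tests and discharge plausible, though no discharge criterion is stated.

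**Conclusion.** The point holds for patients with at least two post-initiation tests. The clearance percentage has no common assessment day. Patients unresolved at the end of observation, including those who die before clearance, are non-events in it but censored in section 9.3.8. The percentage therefore mixes speed of clearance with length of stay.

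Size and direction cannot be fixed from the protocol, which gives no length of stay and no discharge criterion. With independent discharge and a constant hazard, a 25% change in stay moves the planned 20% by −4.6 or +4.3 points, against half widths of 2.77 and 3.50 points. With discharge that waits for clearance, the percentage moves towards 100%. These are illustrations under assumptions, not predictions. The consequence is a secondary descriptive result that is hard to interpret or to compare between subgroups or with other studies. The precision arithmetic and the primary safety analysis are not affected.

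**What to change.** **Section 9.7.3.2.** Add the cumulative percentage cleared with 95% CI at prespecified days from the index date, for example days 7, 14 and 28, from the time-to-event analysis. Treat death before clearance as a competing event. Keep the observed percentage, label it as by end of observation, and show beside it the distribution of observation time and the number whose observation ended without clearance.

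**Section 9.3.8.** Censor patients without the event at the last date on which the event could still have been confirmed, in place of the end-of-observation date.

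**Section 9.5.** State the day or observation window to which the 20% refers.

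**Section 9.9.** Name variable follow-up as a limitation, and say that discharge linked to test results would be informative censoring that these changes do not remove.

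**Cost.** Protocol and SAP wording only. Test dates and results and the discharge date are already to be abstracted (section 9.3, Table 1). Late-day estimates will rest on few patients still under observation and will have wide intervals.

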9.7.4. Subgroup analysis

If data are adequate, subgroup analyses for the variables assessing safety, treatment patterns and effectiveness may be performed. Specifically,

- For safety variables, subgroup analyses will be performed by vaccination status, baseline COVID-19 severity, risk factors, renal impairment, hepatic impairment, and use of prior COVID-19-related treatments (described in section 9.3).
- For treatment patterns variables, subgroup analyses will be performed by vaccination status, baseline COVID-19 severity, risk factors, renal impairment, hepatic impairment, use of prior COVID-19-related treatments and administration time since onset of the first COVID-19 symptom/sign (described in section 9.3).
- For effectiveness variables, subgroup analyses will be performed by vaccination status, baseline COVID-19 severity, risk factors, renal impairment, hepatic impairment, use of prior COVID-19-related treatments and administration time since onset of the first COVID-19 symptom/sign (described in section 9.3).

9.7.5. Interim analyses

One interim analysis is planned to be conducted with the report expected to be available in May 2023. At this interim analysis, safety, treatment patterns and effectiveness with respect to all endpoints will be assessed.

9.8. Quality control

All participants data relating to the study will be recorded on electronic CRF unless transmitted to the sponsor or designee electronically (eg, laboratory data). The investigator is responsible for verifying that data entries are accurate and correct by electronically signing the CRF.

Guidance on completion of CRFs will be provided in the CRF Completion Requirements document.

The investigator must ensure that the CRFs are securely stored at the study site in encrypted electronic form and are password protected or secured in a locked room to prevent access by unauthorized third parties.

The investigator must permit study related monitoring, audits, IRB/EC review, and regulatory agency inspections and provide direct access to source data documents. This verification may also occur after study completion. It is important that the investigator(s) and their relevant personnel are available during the monitoring visits and possible audits or inspections and that sufficient time is devoted to the process.

Monitoring details describing strategy, including definition of study-critical data items and processes (eg, risk based initiatives in operations and quality such as risk management and mitigation strategies and analytical risk based monitoring), methods, responsibilities, and requirements, including handling of noncompliance issues and monitoring techniques (central, virtual, or onsite monitoring), are provided in the data management plan and monitoring plan maintained and utilized by the sponsor or designee.

The sponsor or designee is responsible for the data management of this study, including quality checking of the data.

Records and documents, including signed ICDs, pertaining to the conduct of this study must be retained by the investigator for 15 years after study completion unless local regulations or institutional policies require a longer retention period. No records may be destroyed during the retention period without the written approval of the sponsor. No records may be transferred to another location or party without written notification to the sponsor. The investigator must ensure that the records continue to be stored securely for as long as they are maintained.

When participant data are to be deleted, the investigator will ensure that all copies of such data are promptly and irrevocably deleted from all systems.

The investigator(s) will notify the sponsor or its agents immediately of any regulatory inspection notification in relation to the study. Furthermore, the investigator will cooperate with the sponsor or its agents to prepare the investigator site for the inspection and will allow the sponsor or its agent, whenever feasible, to be present during the inspection. The investigator site and investigator will promptly resolve any discrepancies that are identified between the study data and the participant's medical records. The investigator will promptly provide copies of the inspection findings to the sponsor or its agent. Before response submission to the regulatory authorities, the investigator will provide the sponsor or its agents with an opportunity to review and comment on responses to any such findings.

